8.2. Secondary Efficacy Analyses

This section describes the planned analyses for the secondary efficacy outcome measures. Where applicable, refer to Section 6.1 for SAS pseudocode. Analyses of mortality will be described in Section 9.4.

Analyses of the key secondary outcome measure will be explored in the specified subgroups described in Section 6.4. Analyses of the other secondary outcome measures will be performed by treatment arm only and repeated for specified subgroups described in Section 6.4 and Section 6.7 via stratified analyses. As with the analyses described in Section 8.1.2, tabular summaries will follow the structure of the main tabular summaries planned for each outcome with the modification that stratified estimates will be provided in separate rows. Forest plots will display confidence intervals of outcomes/estimates across subgroups, where applicable.

All secondary efficacy analyses will be performed in the ITT population. As Treated analyses will be explored to investigate consistency of results compared to the ITT analyses.

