8.1.2. Supplemental and Sensitivity Analyses

For all supplemental and sensitivity analyses of the primary outcome, p-values may or may not be reported, and 95% confidence levels will be used for confidence interval estimates.

The primary analysis will be repeated in the As Treated analysis population where subjects who are not treated will be censored at enrollment. The tabular and graphical summaries described in the previous section will be replicated for this As Treated analysis.

Sensitivity analyses will be performed using Cox proportional hazards models to estimate the hazard ratio. First, an ITT analysis will be performed in which subjects who die prior to recovering are treated as experiencing a competing risk in the Fine-Gray proportional hazards regression model. Second, a Cox model will be fit with binary indicators for treatment group and disease severity Moderate vs. Severe [separate models for randomized stratum and actual stratum] as well as a treatment * disease severity interaction term. The models will be fit to the ITT analysis population. The treatment group hazard ratios and CIs will be reported for both sets of models and the interaction term p-value will be reported for the interaction models. As requested by the DSMB, a restricted mean survival time analysis will be performed as an exploratory analysis. The restricted mean recovery time estimates will be provided for each treatment group and randomized disease severity stratum as well as the difference in restricted mean recovery time between treatment groups within each of the severity strata (Table 18). Time to recovery will also be explored within prior Remdesivir treatment subgroups (Any Treatment vs. No Treatment) (Table 19).

The primary analysis will also be repeated using the other subgroups defined in Section 6.4 in place of disease severity. Each subgroup will be considered separately and the tabular and graphical summaries described in the previous section will be replicated for each subgroup. The tabular summary will also include results from an analysis of time to recovery controlling for age

and duration of symptoms as continuous covariates and baseline d-dimer and CRP values as continuous covariates. A forest plot will be generated to display the overall treatment hazard ratio estimate and CI from each of the within-stratum analyses (Table 20 and Table 21). These analyses will be performed in the ITT and As Treated populations.

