8.2.1. Ordinal Scale Outcomes (Key Secondary Outcome Measure)

For the analysis of the key secondary outcome measure, the distribution of the 8-point ordinal clinical status scale with 8 categories at Study Visit Day 15 (not necessarily actual study day 15), the outcome will be analyzed using a proportional odds model with treatment arm and disease severity as covariates. The treatment odds ratio estimated from the model will be presented along with the p-value (Table 25). The Study Visit Day 15 clinical status score will be depicted graphically using shifted bar plots; the outcomes will be presented by baseline ordinal score and treatment group (Figure 13). In addition to the subgroup analyses, the main analysis will be

repeated including a treatment * disease severity interaction term, where the interaction term p-value will be reported for the interaction model.

Multiple supplemental analysis of this key secondary outcome will be performed. Time to improvement by at least one category in the clinical status 8-point scale (see Section 3.3). The log rank test will be performed using a Cox proportional hazards model to test whether the curves differ between treatment arms. The median time to event and CI in each treatment group will be summarized along with the treatment hazard ratio estimate and log rank p-value (Table 27). Differences in time-to-event endpoints by treatment arm will be summarized with Kaplan-Meier curves (Figure 16). Number at risk, hazard ratio and log rank p-values will be presented on the figures. The analyses (and tabular and graphical summaries) will be repeated using the outcome of time to improvement in two categories of the ordinal scale defined in Section 3.3. In addition, a subgroup analysis time to improvement among subjects enrolled with a clinical score of 7 will be performed using the retreatment censoring plan.

The above analyses will be repeated with the modification to the ordinal scale described in Section 4.3 (Table 28).

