	Baricitinib + RDV (N=X)	Severe	x	x.x	x.x, x.x	x.xx	x.xx, x.xx	--
	Placebo + RDV (N=X)		x	x.x	x.x, x.x			
	Baricitinib + RDV (N=X)	Any Severity	x	x.x	x.x, x.x	x.xx	x.xx, x.xx	0.xxx
	Placebo + RDV (N=X)		x	x.x	x.x, x.x			

Repeat for the As Treated Population.

N= Number of subjects in the specified treatment group, disease severity, and analysis population.
n = Number of recovered subjects.
HR is the ratio of the hazard of recovery in each treatment group estimated from the Cox model. The ratio is Baricitinib + RDV to Placebo + RDV.
HR for the ‘Any Severity’ group is the hazard ratio from the stratified Cox Model.
P-value calculated using the stratified log-rank test

Tables with similar format:

Table 16: Time to Recovery by Treatment Group and Randomized Disease Severity: Fine-Gray, Covariate-Adjusted, and Interaction Modeling

Table 17: Time to Recovery by Treatment Group and Baseline Ordinal Score: Fine-Gray and Interaction Modeling

Programming Notes for Table 16 and Table 17:

For both tables, the median time columns will be excluded.

The “Analysis Population” column will be replaced by a “Model” column. For the Fine-Gray estimates, the column will display “Fine-Gray”, for the covariate-adjusted model, the column will display “Covariate-Adjusted”, and for the interaction models (Table 16), the columns will display, respectively, for the three models to be run:

- “Treatment-Severity Interaction (Randomized Severity)”
- “Treatment-Severity Interaction (Actual Severity)”

For the interaction models, the p-value for the interaction term will be provided in a footnote reading “The p-value for the treatment by [randomized/actual] disease severity interaction term was 0.xxxx.”.

For the covariate-adjusted model, a cox model will be run with age, duration of symptoms prior to enrollment, baseline d-dimer, and baseline CRP values included as continuous covariates.

For Table 17, the interaction model column will display “Baseline Ordinal Score Interaction”. For the interaction models, the p-value for the interaction term will be provided in a footnote reading “The p-value for the treatment by baseline ordinal score interaction term was 0.xxxx.”.

Table 18: Time to Recovery by Treatment Group and Disease Severity: Restricted Mean Survival Time Analysis – ITT Population

Analysis Population	Treatment Group	Randomized Disease Severity	n	Restricted Mean Recovery Time		Difference	
				Estimate	95% CI	Estimate	95% CI

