Programming Note: P-value of treatment comparison will only be displayed for the main analysis. For the interaction models, the p-value for the interaction term will be provided in a footnote reading “The p-value for the treatment by disease severity interaction term was 0.xxxx.”.

Table 27: Time to Improvement on the 8-Point Ordinal Scale by Treatment Group

Analysis Population	Treatment Group	Median Time			HR		P-value
		n	Estimate	95% CI	Estimate	95% CI	
Improvement by at least One Category							
ITT Population	Baricitinib + RDV (N=X)	x	x.x	x.x, x.x	x.xx	x.xx, x.xx	x.xxx
	Placebo + RDV (N=X)	x	x.x	x.x, x.x			
As Treated Population	Baricitinib + RDV (N=X)	x	x.x	x.x, x.x	x.xx	x.xx, x.xx	x.xxx
	Placebo + RDV (N=X)	x	x.x	x.x, x.x			
Improvement by at least Two Categories							
ITT Population	Baricitinib + RDV (N=X)	x	x.x	x.x, x.x	x.xx	x.xx, x.xx	x.xxx
	Placebo + RDV (N=X)	x	x.x	x.x, x.x			
As Treated Population	Baricitinib + RDV (N=X)	x	x.x	x.x, x.x	x.xx	x.xx, x.xx	x.xxx
	Placebo + RDV (N=X)	x	x.x	x.x, x.x			

N = Number of subjects in the specified treatment group and analysis population.
n = Number of subjects with improvement.
HR is the ratio of the hazard of improvement in each treatment group estimated from the Cox model. The ratio is Baricitinib + RDV to Placebo + RDV.
P-value calculated using the Log-rank test

Tables with similar format:

Table 28: Time to Improvement on the 8-Point Ordinal Scale by Treatment Group: Modified Ordinal Scale

Table 29: Time to Improvement by at least One Clinical Status Category on the 8-Point Ordinal Scale by Treatment Group within Subgroups – ITT Population

Table 30: Time to Improvement by at least One Clinical Status Category on the 8-Point Ordinal Scale by Treatment Group within Subgroups – As Treated Population

Table 31: Time to Improvement by at least Two Clinical Status Categories on the 8-Point Ordinal Scale by Treatment Group within Subgroups – ITT Population

Table 32: Time to Improvement by at least Two Clinical Status Categories on the 8-Point Ordinal Scale by Treatment Group within Subgroups – As Treated Population

Programming notes for Table 28:

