	Placebo + RDV (N=X)		x	x.x	x.x, x.x			

N= Number of subjects in the specified treatment group and analysis population.

n = Number of subjects who died by the specified study day.

HR is the ratio of the hazard of Death in each treatment group estimated from the stratified Cox model. The ratio is Baricitinib + RDV to Placebo + RDV.

P-value calculated using the stratified Log-rank test.

Tables with similar format:

Table 67: Time to Death through Day 15 and 29 by Treatment Group and Actual Disease Severity – As Treated Population

Table 68: Time to Death through Day 15 and 29 by Treatment Group within Subgroups – ITT Population

Table 69: Time to Death through Day 15 and 29 by Treatment Group: Medications of Interest Sensitivity Analysis – ITT Population

Table 70: Time to Death through Day 15 and 29 by Treatment Group: Interaction Modeling – ITT Population

Programming notes for Table 68:

Log-rank p-values will not be included in this table so the column will be removed. The Disease Severity column will be removed and to the left of the Study Day column, a column titled “Analysis/Subgroup” will be inserted. Rows will be generated for each subgroup.

Programming notes for Table 69:

Log-rank p-values will not be included in this table so the column will be removed. The table will include a column to the left of the “n” column titled “m”. The corresponding footnote will read “m = Number of subjects reporting use of the medication of interest.” The Disease Severity column will be removed and a “Medication of Interest” column will be inserted to the left of Study Day. Separate models will be fit for the following categories of medications (see Section 6.4):

- Any Medication of Interest
- Hydroxychloroquine/Chloroquine
- Corticosteroids
- Anti-Inflammatory Drugs

The table will include the following footnote: “In this analysis, subjects that reported use of the specified medications of interest (Section 6.4 of the SAP) are censored at time of medication receipt.”

Programming notes for Table 70:

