N = Number of Subject in the As Treated Population and specified actual disease severity stratum. n = Number of subjects in a given treatment group who experienced the specified safety event outcome. 95% CI calculated using C-P/Blaker method P-value calculated using Barnard's Exact Test							

Table 73: Analysis of Time to Death, SAEs, or Grade 3 or 4 AEs by Treatment Group – As Treated Population

Actual Disease Severity	Treatment Group	n	Median Time		HR		P-value
			Estimate	95% CI	Estimate	95% CI	
Any Severity (N=X)	Baricitinib + RDV (N=X)	X	x.x	x.x, x.x	x.xx	x.xx, x.xx	x.xxx
	Placebo + RDV (N=X)	X	x.x	x.x, x.x			
Moderate (N=X)	Baricitinib + RDV (N=X)	X	x.x	x.x, x.x	x.xx	x.xx, x.xx	--
	Placebo + RDV (N=X)	X	x.x	x.x, x.x			
Severe (N=X)	Baricitinib + RDV (N=X)	X	x.x	x.x, x.x	x.xx	x.xx, x.xx	--
	Placebo + RDV (N=X)	X	x.x	x.x, x.x			

N= Number of subjects in the As Treated Population and specified actual disease severity stratum.

n = Number of subjects who died or experienced SAEs or Grade 3 or 4 AEs.

HR is the ratio of the hazard of Death/SAE/AE of Grade 3 or 4 in each treatment group estimated from the stratified Cox model. The ratio is Baricitinib + RDV to Placebo + RDV. P-value calculated using the Log-rank test

Table 74: Infections by Treatment Group – As Treated Population, Moderate Disease Severity

Anatomical Location	Pathogen	Baricitinib + RDV (N=X)									Placebo + RDV (N=X)								
		Severe			Life-Threatening			Death			Severe			Life-Threatening			Death		
		n	%	Events	n	%	Events	n	%	Events	n	%	Events	n	%	Events	n	%	Events
Any Location	Any Pathogen	x	x	x	x	x	X	x	x	x	x	x	x	x	x	x	x	x	x
Location 1	Any Pathogen	x	x	x	x	x	X	x	x	x	x	x	x	x	x	x	x	x	x
	Pathogen 1	x	x	x	x	x	X	x	x	x	x	x	x	x	x	x	x	x	x
	Pathogen 2	x	x	x	x	x	X	x	x	x	x	x	x	x	x	x	x	x	x
Location 2	Any Pathogen	x	x	x	x	x	X	x	x	x	x	x	x	x	x	x	x	x	x
	Pathogen 1	x	x	x	x	x	X	x	x	x	x	x	x	x	x	x	x	x	x
	Pathogen 2	x	x	x	x	x	X	x	x	x	x	x	x	x	x	x	x	x	x

Note: Percents may not add to 100 because participants may have infections with multiple pathogens. All Grade 3 or 4 infections are also reported as AEs.
 N=Number of participants randomized to Treatment group.
 n=Number of participants with infection.

Tables with similar format:

Table 75: Opportunistic Infections by Treatment Group – As Treated Population, Moderate Disease Severity

Table 76: Infections by Treatment Group – As Treated Population, Severe Disease Severity

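### Time to improvement, time to discharge or NEWS ≤2, and most recovery subgroup hazard ratios drop the severity stratum used in randomisation

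*SAP*

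**What the plan says.** SAP 4.2.3 stratifies randomisation by site and by severity (ordinal 4/5 against 6/7). After that the SAP treats severity in three ways.

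**Kept.**
- Primary analysis, Table 15: "P-value calculated using the stratified log-rank test".
- Key secondary, SAP 8.2.1: "using a proportional odds model with treatment arm and disease severity as covariates".
- Mortality, Table 66: "P-value calculated using the stratified Log-rank test".

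**Dropped.**
- SAP 8.2: "Analyses of the other secondary outcome measures will be performed by treatment arm only and repeated for specified subgroups".
- Tables 27 (time to improvement) and 37 (time to discharge or NEWS ≤2) take the hazard ratio from a Cox model with no strata named, and footnote the test as "P-value calculated using the Log-rank test". Table 28 follows the Table 27 format.
- Recovery subgroups, SAP 8.1.2: "The primary analysis will also be repeated using the other subgroups defined in Section 6.4 in place of disease severity". The notes to Tables 20–21 remove the severity column and the any-severity rows. In Table 15 only the any-severity row used the stratified Cox model.

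**Mixed or silent.**
- Table 73 (death, SAE or Grade 3–4 AE) has a hazard ratio "estimated from the stratified Cox model. The ratio is Baricitinib + RDV to Placebo + RDV. P-value calculated using the Log-rank test", so the model is stratified and the test is not described as such.
- The Table 68 note reads "The Disease Severity column will be removed and to the left of the Study Day column" (where a subgroup column goes in), without saying whether the Table 66 model stays stratified.

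SAP 6.1 gives stratified code for the final time-to-event analyses but lets the strata line be removed for unstratified ones, without listing which those are.

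**The concern.** An analysis should normally condition on the factor that stratified the randomisation. Omitting a prognostic stratum has two effects on a log-rank or Cox analysis:

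- **Attenuation.** Patients who recover quickly leave the risk set sooner, and they do so faster in the better arm. That arm's later risk set is then weighted towards slow recoverers. The pooled hazard ratio falls below the common within-stratum ratio even when the arms are perfectly balanced.
- **Conservatism.** Stratified randomisation removes the between-stratum part of the variation in the test numerator, but the unstratified variance still counts it. The test then rejects less often than its nominal level.

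For time to discharge or NEWS ≤2, the scoring makes it plausible that severity is prognostic. Protocol Appendix B 8.1.2.3 gives 2 points for any supplemental oxygen and fixes respiratory rate at 3 points for ventilated or ECMO subjects. A subject at ordinal 7 therefore cannot score 2 or less while in that state. For time to improvement, which is measured from each subject's own baseline, the strength is less certain.

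The recovery subgroup tables show no p-values, so attenuation is the main effect there. The age, sex, race, region, comorbidity and symptom-duration rows would estimate a marginal ratio and appear in a forest plot beside a severity-stratified overall ratio. Severity is also not balanced by design within those levels (site stratification helps only for region), so chance imbalance can move a row either way.

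**Working it through.** **1. The plan's own figure.** SAP 5 gives E = 4(1.96 + z_β)² / (ln θ)². With θ = 1.25, ln θ = 0.2231 and z_β = 1.036 for 85% power, E = 4 × 2.996² / 0.0498 = 721. Rounding z_β to 1.04 gives 4 × 3.00² / 0.0498 = 723, the stated number. Then 723 / 0.70 = 1032.9, against the stated 1032. The primary design reproduces and this point does not affect it.

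**2. The comparison.** The stratified statistic is that of SAP 8.1.1: O − E and V are formed within each severity stratum and then summed. The unstratified statistic uses the same terms from one pooled risk set.

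**3. Inputs.** From the documents: N = 1032, 1:1 allocation, two-sided 5%, ratio 1.25. The last is the design value for recovery, borrowed here because none is given for these endpoints. Assumed, because the documents give neither: the share of severe patients and the severe-to-moderate event-rate ratio. Also assumed: exponential times, exact 1:1 balance within severity, and the same treatment ratio in both strata.

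**4. Simulation A.** Pooled event proportion calibrated to 70% by Day 28; 2,000 trials per cell (Monte Carlo standard error about 0.8 points at 85% power). Power is unstratified / stratified; HR is unstratified. The stratified HR was 1.25 throughout.

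| Moderate:severe rate ratio | 20% severe | 33% severe | 50% severe |
|---|---|---|---|
| 1 | 85.0 / 84.9, HR 1.25 | 84.4 / 84.1, HR 1.25 | 86.0 / 85.7, HR 1.25 |
| 2 | 82.7 / 84.7, HR 1.24 | 81.1 / 84.3, HR 1.24 | 82.7 / 85.6, HR 1.24 |
| 4 | 79.5 / 85.5, HR 1.22 | 74.5 / 84.9, HR 1.21 | 70.0 / 85.4, HR 1.19 |
| 6 | 75.4 / 84.5, HR 1.21 | 64.4 / 85.0, HR 1.18 | 52.7 / 85.3, HR 1.16 |

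Under the null at ratio 4 (4,000 trials), unstratified rejection was 2.9% (33% severe) and 2.3% (50% severe), against about 5.5% stratified.

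**5. Simulation B.** Event times grouped by day, 30–50% severe, moderate control median 5 or 8 days, 20,000 trials per cell. Stratified hazard ratios were 1.24–1.26 and stratified null rejection 4.7–5.3%.

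| Severe:moderate rate ratio | Power lost (points) | Unstratified HR | Unstratified null rejection |
|---|---|---|---|
| 1.0 | 0 | 1.24–1.26 | about 5% |
| 0.6 | 1.4–1.9 | 1.23–1.24 | 4.3–4.6% |
| 0.4 | 5.4–6.8 | 1.21–1.22 | 3.1–3.5% |
| 0.25 | 13–18 | 1.18–1.20 | 1.9–2.2% |
| 0.15 | 24–37 | 1.15–1.17 | 0.8–1.2% |

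**6. Cross-check of one cell** (40% severe, moderate median 8 days, rate ratio 0.25). Mean Z was 2.45 unstratified and 3.11 stratified. Stratified power ≈ Φ(3.11 − 1.96) = Φ(1.15) = 87.5%; simulated 87.6%. A null rejection of about 2% implies that the unstratified Z has standard deviation about 1.96 / 2.33 = 0.84. Power is then ≈ Φ((2.45 − 1.96) / 0.84) = Φ(0.58) = 72%; simulated 72.1%. The loss is 87.6 − 72.1 = 15.5 points.

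**7. Cost of stratifying inside a subgroup level.** The ratio of stratified to unstratified standard error was 1.03 at 60 subjects, 1.01 at 150 and at most 1.005 at 500. At rate ratio 0.25 the median hazard ratio was 1.19 unstratified and 1.25–1.26 stratified.

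**The case against.** The strongest reply is that the SAP never calls these analyses unstratified. SAP 6.1 presents stratified code for final time-to-event analyses, SAP 8.2 refers back to it, and the mortality text in SAP 9.4 also omits the word although Table 66 is stratified. That shows the wording is loose, but it does not settle the matter. Section 6.1 allows the strata line to be dropped, and the more specific text in 8.2 says arm only. The Table 66 footnote does carry the word that Tables 27 and 37 lack. The mention of stratified analyses in 8.2 describes the subgroup repeats, shown in separate rows, and not the overall test.

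Other points stand in part:

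- **Consequence is limited.** Time to improvement is described as supplemental to the key secondary, and secondary analyses carry no multiplicity adjustment.
- **Severity-specific results are planned** (Tables 29–32 and 38–39; baseline-score curves in Figures 17–24 and 28–31). A reader could combine two stratum-specific ratios by inverse variance, but no pooled severity-stratified estimate or test is planned.
- **Unadjusted forest-plot rows are common practice**, and a marginal ratio is a different estimand, not an error. The mismatch with the stratified overall estimate remains.
- **The losses shrink with fewer severe patients.** At rate ratio 0.25 a further simulation gave 7–12 points at 20% severe and 2–6 at 10% severe. The 0.15 row has no support in the documents.
- **Tables 68 and 73 are small wording items.** Table 68 can fairly be read as inheriting the Table 66 model.

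**Conclusion.** The concern holds. As written, Tables 27, 28 and 37 and the recovery subgroup rows not defined by severity or baseline score leave out the randomisation stratum that the primary, key secondary and mortality analyses keep. Among the Section 6.4 subgroups for the other secondary outcomes, only symptom duration is affected. Subgroups defined by severity or baseline score already condition on it.

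The direction is certain if severity is prognostic: attenuation and a conservative test. The size is illustrative. It runs from nothing, through 2–7 points of power at moderate prognostic strength (moderate rate about 1.7 to 2.5 times the severe rate), to roughly 6–18 points when the moderate rate is four times the severe rate and 20–50% are severe. This is worth correcting for efficiency, consistency and clear prespecification. It does not threaten the primary conclusion or the type I error rate.

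**What to change.** - **SAP 8.2, Tables 27, 28 and 37:** specify the log-rank test and Cox model stratified by randomised severity, as in Tables 15 and 66.
- **SAP 8.1.2, Tables 20–21:** replace the substitution of subgroup for severity with an analysis within each subgroup level, stratified by severity. Exempt subgroups defined by severity or baseline ordinal score.
- **Secondary time-to-event outcomes:** do the same for the symptom-duration subgroups, and for any regional repeats arising from the reference in 8.2 to Section 6.7.
- **Table 73:** stratify the log-rank test by actual severity, to match its Cox model.
- **Table 68:** state that the stratified model is kept. Table 19 (prior remdesivir), which also names only a Cox model, can be clarified in the same edit.
- **SAP 6.1:** list which analyses, if any, drop the strata line.

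The change should be made before unblinding. It needs no new data, only SAP wording and the strata line already in the code. The price is sparse strata in very small subgroup levels, with intervals about 3% wider on the log scale at 60 subjects and 0.5% or less at 500.
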